5.1 Imputation rules

No imputation will be done for missing endpoints.

5.1.1 Study drug

In case of missing or partial start date of the first study drug application, the start date should be shifted to the earliest possible date, but not earlier than screening visit.

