#### Confidential Protocol No. CAMG334ADE03

#### Table 8-1Assessment Schedule

	Screen															Follow up 
Visit number 	0	Baseline	V101	V102	V103	V104	V105	V106	V107	V108	V109	V110	V199	V201 – V20X	V101B	V301
End of week	-2 to 0	0	12	24	36	48	60	72	84	96	108	120	128	Every 12 weeks	NA	132
Obtain informed consent	х															
Demography	Х															
Medical history & prior medication 	х															
Complete Physical Exam	S												S		S	
Brief Physical Exam		S	S	S	S	S	S	S	S	S	S	S		S		S
Height	Х															
Weight	Х												Х		Х	
Vital Signs 	Х	Х	Х	Х	Х	Х	Х	Х	Х	Х	Х	Х	Х	Х	Х	Х
ECG	Х														Х	
Concomitant Medications		x	x	x	x	x	х	х	х	x	х	х	х	х	x	

Page 31

	Screen		During drug holiday	First visit after drug holiday	Follow up 											
Visit number 	0	Baseline	V101	V102	V103	V104	V105	V106	V107	V108	V109	V110	V199	V201 – V20X	V101B	V301
End of week	-2 to 0	0	12	24	36	48	60	72	84	96	108	120	128	Every 12 weeks	NA	132
Adverse Events 	Х	х	х	х	х	х	х	х	Х	х	х	х	Х	Х	х	х
Serious Adverse Events⁵	х	x	x	х	х	х	х	х	х	х	х	х	Х	х	x	х
Study Drug dispensing 		х	х	х	Х	Х	Х	х	х	x	х	х			x	
Chemistry/Hematology 8	Х														x	x
Urine pregnancy 		х	x	x	х	х	х	х	х	х	х	х	Х			
Serum Pregnancy	х														x	x
		· 						· 			 	 				

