#### Confidential Protocol No. CAMG334ADE03

Novartis

Clinical trial protocol V01

Page 32

Novartis	Confidential	
Clinical trial protocol V01	Protocol No. CAMG334ADE03	

	Screen					Ope	n-label	Treatm	ent Epo	och				During drug holiday	First visit after drug holiday	Follow up 
Visit number 	0	Baseline	V101	V102	V103	V104	V105	V106	V107	V108	V109	V110	V199	V201 – V20X	V101B	V301
End of week	-2 to 0	0	12	24	36	48	60	72	84	96	108	120	128	Every 12 weeks	NA	132
Open-label Treatment Phase Completion form													х			
Follow-Up Phase Completion form																x

1 – All study visit target dates are to be calculated from the Day 1 visit date and all study procedures for a given visit should be completed on the same day.

2 – The Follow-Up Visit is required 8 weeks after last IMP injection (erenumab). The Follow-Up visit can be skipped if any other safety follow up visit occurred 4 weeks after last study visit. 3 – Including prior prophylactic medication.

4 – Includes blood pressure, pulse and temperature.

5 – SAEs will be collected after signing of the informed consent through the end of the Follow-Up Epoch end of study. Non-serious AEs will be collected starting at Baseline Visit through the end of the Follow-Up Epoch.

6 – Study drug erenumab will be dispensed to the patient at the center during the applicable study visit for home application. Last study drug application will be at week 124.

8 - Should be additionally performed at any visit if deemed necessary by the investigator due to AEs

9 Should be performed/registered by the investigator prior to dosing during DBTE.

X = Assessment to be recorded in the source documents and the clinical data base; S = Assessment to be recorded as source documentation only.

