1.1 Study design

This is an open-label, multi center, single arm study with flexible dosing allowing both dose adjustment and one drug holiday per patient.

The study design consists of 3 parts:

• Screening Epoch (0 - 2 weeks): required for all patients to assess initial eligibility.

• **Open-label Treatment Epoch** (128 weeks): Individual patients are treated for 128 weeks in the open-label treatment phase. During this open-label Treatment Epoch the erenumab dose may be adjusted from 70 mg to 140 mg or vice versa by discretion of the physician at any scheduled study visit. Additionally, a voluntary single treatment interruption ('drug holiday') of up to 24 weeks (approximately six months) may be introduced after at least 12 weeks of treatment in the open-label Treatment Epoch.

• Follow-up Epoch (4 weeks): A Follow-Up Visit 4 weeks after the last regular study visit (8 weeks after last IMP application) will be required as part of routine safety monitoring.

End of trial will occur when the last patient completes last visit (LPLV).

This 128-week open-label study will provide further treatment to patients still blinded for the randomization of the study CAMG334ADE01. In general, the 750 subjects randomized for clinical trial CAMG334ADE01 will be eligible for participation in the open-label study. It is estimated that approximately 75% to 85% of the study population meaning 563~638 subjects will enroll in the open-label study.

This is a single arm study. All patients will receive Erenumab. No randomization is required.

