2.1.1.1 Study dates

First IMP Dose Date

The first IMP dose date is the date on which a subject is administered the first dose of erenumab following screening. For subjects who are screened but no dose administration is documented, first IMP Dose Date is considered missing.

Last IMP Dose Date

The last IMP dose date for each subject is defined as the latest date of a dose administration.

Time under treatment

Time under treatment is defined as (Last IMP Dose Date + 28 – First IMP Dose Date) - Duration of treatment interruption due to drug holiday (if applicable).

Exposure-adjusted incidence rate of AE

Exposure-adjusted patient incidence rate of AE is defined as the total number of patients who reported an AE in a given time period of follow up divided by total patient-years of exposure in that period.

Total patient-years of exposure is defined as the sum of the duration of exposure from first IMP dose to the earliest of end-of-study date, end-of-OLTP date, or first report of event across all patients during the OLTP.

Study Day

Study Day 1 is defined as the first IMP dose date. For patients who are screened but not dosed after inclusion, Study Day 1 is defined as the date of screening visit.

Study Day is defined as the number of days from Study Day 1.
Before Study Day 1:
Study Day = (Date of Interest – Date of Study Day 1)

On or after Study Day 1: Study Day = (Date of Interest – Date of Study Day 1) + 1

Therefore the day prior to Study Day 1 is Day -1.

Drug holiday

Drug holiday is defined as a voluntary single treatment interruption of up to 24 weeks introduced after at least 12 weeks of treatment in the open-label Treatment Epoch.

After the "Planned date of last dose before drug holiday" starts a 28 day drug holiday initiation period, followed by the actual drug holiday period (see definitions below).

Drug holiday planned

Drug holiday is defined as planned if in the eCRF "Planned date of last dose before drug holiday" is not missing.

Drug holiday started

Drug holiday is defined as started if in the eCRF "Planned date of last dose before drug holiday" is not missing and lies at least 4 weeks before the cut-off date (regarding the interim analysis) resp. end of study date and up to day 28 after the "Planned date of last dose before drug holiday" no IMP application is documented.

Return to treatment after drug holiday

Patients are defined as returned after drug holiday if in the eCRF "Date of first dose after drug holiday" is not missing.

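### SAP 5.1.1 allows an incomplete first-dose date to be imputed back to the screening visit, up to 14 days before study drug is first dispensed

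*SAP*

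**What the plan says.** SAP 5.1.1 covers a first study drug application whose date is missing or partial: "the start date should be shifted to the earliest possible date, but not earlier than screening visit". The screening visit is the only floor given.

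The surrounding text fixes when a first dose is possible:

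- SAP 1.1 and Protocol section 3 describe a Screening Epoch of 0 to 2 weeks, "required for all patients to assess initial eligibility". Protocol Figure 3-1 ends it on Day -1.
- In Protocol Table 8-1 the row "Study Drug dispensing" is blank at Screening and first marked at Baseline. Footnote 6 adds: "Study drug erenumab will be dispensed to the patient at the center during the applicable study visit for home application".
- SAP 2.1.1.1 states: "The first IMP dose date is the date on which a subject is administered the first dose of erenumab following screening". It treats the date as missing only for screened subjects with no documented administration.

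The first dose date is then used widely. In SAP 2.1.1.1 it defines Study Day 1 and starts time under treatment, the patient-years of exposure and the on-treatment period. In SAP 2.1.1.4 it is the cut for treatment-emergent AEs and starts the duration of exposure. Through Study Day 1 it is the floor for imputed AE start dates in SAP 5.1.2.

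**The concern.** Drug is handed out at the Baseline Visit and injected at home, so no dose of this study's supply can be taken before that visit. A rule that stops only at screening can therefore produce a date on which the patient could not have been dosed. This is a stated rule that gives a wrong date, not a missing detail.

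Two things follow for an affected patient. Untreated days enter the exposure denominator. In addition, SAEs are collected from informed consent (Table 8-1, footnote 5), so an SAE in the screening period could fall after the imputed first dose and be reported as treatment-emergent. In a single-arm study with safety as its primary objective, an event before any study drug should not be in that count.

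**Working it through.** **Check of the timeline.** Footnote 6 to Table 8-1 says "Last study drug application will be at week 124". SAP 2.1.1.1 computes time under treatment as last dose date + 28 − first dose date, less any drug holiday. With no holiday this is 124 × 7 + 28 = 896 days = 128 weeks, which matches the stated Treatment Epoch.

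**Size of the date error.** Let g be the screening-to-Baseline gap in days (0 to 14) and d the day of the month of the Baseline Visit, with the first dose taken that day.

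- Only the day missing: shift before Baseline = min(d − 1, g). This borrows the first-of-month meaning of earliest possible date from SAP 5.1.2, where it is defined for AE dates; 5.1.1 does not define the term.
- Dose documented but whole date missing: shift = g.

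Example: screening 6 March, Baseline and dispensing 20 March, dose recorded only as March. The rule gives the later of 1 March and 6 March, which is 6 March, 14 days before dispensing.

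The documents do not give the distribution of g. If g is uniform on 0 to 14 and d uniform on 1 to 30 (assumptions), the share shifted with only the day missing is (14/15) × (29/30) = 90%, with a mean of about 5.8 days. With the whole date missing it is 14/15 = 93%, with a mean of 7.0 days. If screening and Baseline fall on the same day, the shift is 0.

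**Effect on time under treatment, 14-day shift, last dose date complete where there is more than one dose**

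| Patient | Correct | After shift | Change |
|---|---|---|---|
| Completer, no holiday | 896 days | 910 days | 14/896 = 1.6% |
| Two doses, 28 days apart | 56 days | 70 days | 14/56 = 25% |
| One dose | 28 days | 28 days | none |

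The one-dose patient is unchanged because first and last dose are the same administration, so both dates move together.

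**Pooled effect.** Let f be the share of patients affected (not in the documents; 1% to 5% assumed). At the 14-day maximum:

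- f = 1%: 0.01 × 14/896 = 0.016%
- f = 5%: 0.05 × 14/896 = 0.078%
- f = 5%, every patient taking a full 24-week holiday: 896 − 168 = 728 days, and 0.05 × 14/728 = 0.096%

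At the mean shift of 5.76 days, 5 to 25 of 500 patients contribute about 29 to 144 person-days. The upper figure is 144/(500 × 896) = 0.03% of the total.

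SAP 2.1.1.1 also defines patient-years that stop at the first event. With a constant hazard matching the 87% with an AE over three years cited in Protocol 12.8.1 (assumption), the mean is about 436 days. A 14-day shift is then 14/436 = 3.2% per affected patient, or 0.03% to 0.16% pooled for f of 1% to 5%.

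**The case against.** The strongest reply is that nothing material follows. Much of it stands.

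- **Frequency.** No text suggests that incomplete first-dose dates are common. Missing values are queried (Protocol 11.2), data for primary variables are fully verified (11.3), and compliance is reviewed at each visit (6.5.1). The 1% to 5% range is only an assumption.
- **Treatment-emergent AEs.** Footnote 5 to Table 8-1 starts non-serious AE collection at Baseline, although the table also marks AEs at Screening. In practice mainly screening-period SAEs are exposed. At an assumed 5 to 10 SAEs per 100 person-years, 29 to 144 person-days (0.08 to 0.39 person-years) would give about 0.004 to 0.04 such SAEs in the whole trial.
- **Caution.** An early first-dose date counts more events as treatment-emergent, which is a defensible convention. That reasoning ends at dispensing. Going further back also adds untreated days to the denominator, which lowers the rate.

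Three stronger readings are tempting and not supported:

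- A reader might infer that a one-dose patient's exposure rises by half, from 28 to 42 days. Under the time-under-treatment formula the shift cancels.
- A reader might infer that Baseline Visit vital signs, which could carry Study Day 15, would be analysed as post-dose. SAP 2.1.1.2 assigns office measurements to the nearest visit window and the next scheduled visit is Week 12, so they would still be expected to map to Baseline. ECG and chemistry/haematology baselines are taken at Screening.
- A reader might infer that every missing date becomes the screening date. SAP 2.1.1.1 leaves it missing when no administration is documented.

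The reply does not remove the error itself. The term earliest possible date cannot be read as already limited by dispensing, because the rule names a different and earlier floor.

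**Conclusion.** The rule is wrong as written, and its effect is small. For a patient with a documented dose and an incomplete date, it can place the first dose up to 14 days before any drug dispensed in this study. The qualification matters because some patients received erenumab in CAMG334ADE01.

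The harm is at patient level: up to 14 untreated days counted as exposure, and a possible false treatment-emergent label on a screening-period SAE. A reader might infer that the primary rate is biased. The documents do not support that: pooled time under treatment moves by less than 0.1% if 1% to 5% of 500 patients are affected and mean exposure is 728 days or more. Under the first-event definition the extreme is about 0.16%. Both rest on an assumed frequency, and the effect is nil where screening and Baseline coincide.

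**What to change.** In SAP 5.1.1, replace the screening visit as the floor with the date of first dispensing (Baseline Visit). When a dose is documented but its whole date is missing, use that dispensing date.

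This keeps the early-date convention and reduces the largest possible shift before dispensing from 14 days to 0. Any delay between dispensing and the home injection stays unknown, as it is now. The cost is one phrase in the SAP. Dispensing already has to be recorded in the Drug Accountability Log (Protocol 6.5.1 and 6.6.1), so no new data are needed, and there is no evident downside.

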5.1.2 AE date imputation

Incomplete day

Incomplete start day will be imputed as MAX(date of study day 1, earliest possible start date).

Incomplete end day will be imputed as MIN(EoS, *latest possible end date*).

Earliest possible start/end date is calculated on the eCRF page and refers to the first day of the corresponding month. *Latest possible start/end date* is calculated on the eCRF page and refers to the last day of the corresponding month.

Incomplete day/month

Incomplete start day/month will be imputed as MAX(date of study day 1, 1st January of the year entered).

Incomplete end day/month will be imputed as MIN(EoS, 31th December of the year entered).

Incomplete day/month/year

Incomplete day/months/year will not be imputed.

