2.1.1.4 Safety endpoints

Safety summaries (tables, figures) include only data from the on-treatment period with the exception of baseline data which will also be summarized where appropriate (e.g. change from baseline summaries). In addition, a separate summary for death including on treatment and post treatment deaths will be provided. In particular, summary tables for adverse events (AEs) will summarize only on-treatment events, with a start date during the on-treatment period (treatment-emergent AEs).

Discontinuation of treatment due to AE during the Treatment Epoch

Discontinuation of treatment due to AE during the Treatment Epoch is determined by the flag on the Treatment Completion eCRF page. "Death" as a reason for treatment discontinuation will be also included in AEs leading to treatment discontinuation.

Treatment-Emergent Adverse Event (TEAE)

Treatment emergent adverse events are defined as AEs occurred on or after the first dose of study treatment. AEs registered prior and after the first dose of study treatment are considered as treatment emergent if they have increased severity based on preferred term any time after the first dose of study treatment.

In case of missing data on a day of AE start date, the AE is considered as treatment emergent if *date of first dose of study treatment* \leq *latest possible start date*

Please, see section 5.1.2 AE date imputation for "latest possible start date" definition.

Serious Adverse Event (SAE)

SAEs are determined by the flag on the Adverse Events eCRF page.

Treatment-Related Adverse Event

Treatment-emergent adverse event is defined as treatment-related, if investigator considered it as having a reasonable possibility to be related to study treatment, which is reflected in the eCRF with a corresponding flag.

Adverse Event leading to dose adjustment

Adverse event is defined as leading to dose adjustment if at least one of the following actions was taken with the study treatment due to AE:

- dose increased
- dose reduced
- drug interrupted
- drug withdrawn

Novartis	Confidential	Page 12 of 34
SAP v1.1		CAMG334ADE03

Duration of exposure to IMP

For all calculations of exposure, dose date refers to receiving dose > 0. The duration of exposure to IMP is computed as min (last IMP dose date + 27, EoS date) – first IMP dose date + 1 either including the time of drug holiday or excluding the time of drug holiday.

Subject Incidence

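### SAP 5.1.2 can date an AE known to precede treatment to Study Day 1, does not agree with the TEAE rule in 2.1.1.4, and leaves fully undated AEs without a default

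*SAP*

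**What the plan says.** Four rules in the SAP act on an incomplete AE start date.

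- **Day missing (SAP 5.1.2):** "Incomplete start day will be imputed as MAX(date of study day 1, earliest possible start date", where the earliest possible date is the first of the month entered.
- **Day and month missing (SAP 5.1.2):** "Incomplete start day/month will be imputed as MAX(date of study day 1, 1st January of the year entered".
- **Whole date missing (SAP 5.1.2):** "Incomplete day/months/year will not be imputed". No classification rule follows.
- **Treatment emergence (SAP 2.1.1.4):** the general definition is "Treatment emergent adverse events are defined as AEs occurred on or after the first dose of study treatment", with a second route for events that worsen after first dose. For incomplete dates there is a separate test: "In case of missing data on a day of AE start date, the AE is considered as treatment emergent if" the first dose date is on or before the latest possible start date. Section 5.1.2 explains that term only for a known month; it "refers to the last day of the corresponding month".

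SAP 2.1.1.4 also states that "summary tables for adverse events (AEs) will summarize only on-treatment events, with a start date during the on-treatment period", and the same sentence treats those events as the treatment-emergent ones. SAP 2.5.2 divides the number of AEs by time under treatment. It does not say whether the imputed date or the TEAE flag decides which AEs count.

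**The concern.** The imputation takes the later of two dates and has no upper limit. When the recorded month or year ends before first dose, the later date is always Study Day 1, so an event known to have started before treatment receives an on-treatment start. A known end date is not consulted either. An AE can therefore begin, by imputation, after it has ended.

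The imputed date and the TEAE test can then give opposite answers for the same AE, although SAP 2.1.1.4 treats the two as equivalent. A programmer could follow either and be within the plan. In the other direction, an AE with no date has nothing to compare with the on-treatment period. At stake are the TEAE flag, the AE tables and the numerator of the primary rate. If the exposure definition in SAP 2.1.1.1 that stops at the first event is used, the denominator is affected as well.

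**Working it through.** The plan gives no count of incomplete AE dates and no expected AE rate per 100 subject-years, so there is no figure of its own to reproduce here. The precision tables in Protocol 12.8 concern proportions of patients and do not enter.

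**Step 1: apply the rules to example dates.** The dates are chosen so that onset can fall after consent, given a screening epoch of up to 14 days (Protocol 3). For first dose on 8 Mar 2021, consent can be as early as 22 Feb 2021. For first dose on 6 Jan 2021, it can be as early as 23 Dec 2020.

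| Case | First dose | Recorded onset | Imputed start (5.1.2) | Latest possible start | TEAE test (2.1.1.4) | On-treatment start date? |
|---|---|---|---|---|---|---|
| A | 8 Mar 2021 | Feb 2021 | MAX(8 Mar, 1 Feb) = 8 Mar | 28 Feb 2021 | fails | yes |
| B | 8 Mar 2021 | Mar 2021, end unknown | MAX(8 Mar, 1 Mar) = 8 Mar | 31 Mar 2021 | passes | yes |
| C | 8 Mar 2021 | Mar 2021, ended 5 Mar | 8 Mar | 31 Mar 2021 | passes | yes |
| D | 6 Jan 2021 | 2020 only | MAX(6 Jan 2021, 1 Jan 2020) = 6 Jan 2021 | not defined | cannot be run | yes |
| E | any | none | none | not defined | cannot be run | cannot be shown |

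- A: the two tests disagree.
- B: the true order is unknown, and counting the AE is the usual conservative choice. This is not a fault.
- C: the AE is treatment-emergent and starts three days after it ended.
- D: the AE is known to pre-date treatment and nothing removes it.
- E: the AE fails a literal reading of the table rule.

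**Step 2: how many records can be affected.** Inputs: SAEs are collected from consent and non-serious AEs from the Baseline visit (Protocol Table 8-1, footnote 5). Drug is dispensed for home use (footnote 6), so first dose may follow that visit. Conditions present at consent are medical history (Protocol 10.1.1), as are AEs from the parent trial (SAP 2.1.1.3 and 2.3.3). Cases A, C and D therefore need an SAE between consent and first dose, or an AE between the Baseline visit and the first home dose.

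Assume onsets spread evenly over the 14 days before Day 1, with first doses spread evenly over the calendar. The mean gap is (1 + 14)/2 = 7.5 days.

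- Share in an earlier month: 7.5 / (365.25/12) = 7.5/30.44 = 24.6%.
- Share in an earlier year: 7.5/365.25 = 2.1%.

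For a 7-day window the mean gap is 4 days, and the shares are 13.1% and 1.1%. These are shares of pre-dose AEs. Only those that also lack the day, or the day and month, are affected.

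**Step 3: effect of one misclassified AE on the primary rate.** Assume every patient completes 128 weeks; the lower exposure applies if every patient also takes a 24-week holiday, leaving 104 weeks.

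- 500 patients: 500 × 128 × 7/365.25 = 1,226.6 subject-years, and 100/1,226.6 = 0.08 per 100 subject-years. With holidays: 500 × 104 × 7/365.25 = 996.6, and 100/996.6 = 0.10.
- 638 patients: 1,565.1 and 1,271.6 subject-years, giving 0.064 and 0.079.

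Early withdrawals would raise these values.

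**The case against.** The best defence is that the plan already screens out most of these records. Parent-trial AEs and conditions present at consent never become AEs, screening lasts at most two weeks, and non-serious AEs are collected only from Baseline. An AE dated months before first dose would normally be medical history. A year-only error requires the pre-dose window to span 31 December. Sites are queried about missing values (Protocol 11.2), and SAP 2.8.1 lists all AEs. All of this stands, and it keeps the point minor.

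A reader might infer that the AE tables necessarily gain false events. The documents do not support that for a missing day: the TEAE test in SAP 2.1.1.4 keeps case A out of the TEAE set, and what remains is an inconsistency between two rules. A reader might also infer that the SAP discards undated AEs. It does not say so. It leaves their classification unstated, and the loss follows only from a literal reading of the table rule.

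Two neighbouring rules invite the same criticism without earning it. SAP 5.1.3 applies the Study Day 1 floor to concomitant drugs, but SAP 2.4.2 reports users by ATC level and preferred name, not new starts. For a first dose date, SAP 5.1.1 says "the start date should be shifted to the earliest possible date, but not earlier than screening visit". Drug is first dispensed at Baseline, so the earliest possible date can be read as that visit. Neither rule changes a meaningful result.

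The defence leaves case C, case D and the missing default for undated AEs unanswered.

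**Conclusion.** The point holds as a minor defect. The stated rules give a contradiction for a missing day, a wrong result when a known end date precedes first dose, no safeguard for a year-only date, and no default for a fully undated AE. The last gap leans towards under-counting, which is the wrong direction in a safety study.

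The total effect cannot be computed because the number of incompletely dated AEs is not given. One misclassified AE is worth 0.064 to 0.10 per 100 subject-years for 500 to 638 patients, assuming all complete treatment. The records exposed are likely few: SAEs after consent, AEs between the Baseline visit and the first home dose, and AEs with no start date. The documents do not support a claim of material bias in the primary rate.

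**What to change.** Amend SAP 5.1.2 and 2.1.1.4 together:

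1. AE start = MIN(latest possible start date, MAX(Study Day 1, earliest possible start date)). Define the latest possible date as 31 December when only the year is known, and never later than a known AE end date. Case A becomes 28 Feb 2021, C becomes 5 Mar 2021 and D becomes 31 Dec 2020, all before first dose. Case B stays at 8 Mar 2021.
2. State that an AE known to have ended before first dose is not treatment-emergent.
3. State that a fully undated AE counts as treatment-emergent unless its end date precedes first dose.
4. State in SAP 2.5.2 that the primary count uses the TEAE flag.

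One caution applies to item 3. SAP 2.1.1.1 also defines patient-years as ending at the first report of an event. If that definition is used with onset dates, an assumed Day 1 onset for an undated AE would cut that patient's time at risk from as much as 128 × 7/365.25 = 2.45 years to about zero. The SAP should rule this out or show a sensitivity analysis.

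The cost is a few lines of SAP text and derivation code. No new data are needed.
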